5.1.11. Local Tolerability Assessment

The Investigator Local Tolerability Assessment will be performed according to the Schedule of Visits and Assessments (Section 1.3).

Application site reactions will be graded at each timepoint. Irritation reactions are graded using the scale detailed in the following section (Berger, 1982). Reactions at the site of product application, which may occur post-Baseline, should be differentiated from the preexisting inflammation associated with the subject's atopic dermatitis.

The investigator assessments will be conducted by the investigator or a properly trained and designated subinvestigator prior to study drug application in the clinic.

Dermal Response

- 0. no evidence of irritation
- 1. minimal erythema, barely perceptible
- 2. definite erythema, readily visible; minimal edema or minimal papular response
- 3. erythema and papules
- 4. definite edema
- 5. erythema, edema and papules
- 6. vesicular eruption
- 7. strong reaction spreading beyond application site

Other Effects

- A. = slight glazed appearance
- B. = marked glazing
- C. = glazing with peeling and cracking
- D. = glazing with fissures
- E. = film of dried serous exudates
- F. = small petechial erosions and/or scabs
- G = no other effects

The Subject Local Tolerability Assessment will be performed according to the Schedule of Visits and Assessments (Section 1.3).

The subject will assess burning/stinging (0-3 score):

Grade	Sensation Following Drug Application
0 (none)	No sensation
1 (mild)	Slight warm, tingling sensation; not really bothersome
2 (moderate)	Definite warm, tingling sensation that is somewhat bothersome
3 (severe)	Hot, tingling/stinging sensation that has caused definite discomfort

This assessment will be administered by the site 10 to 15 minutes after study drug application in the clinic at Baseline and at every clinic visit.

• Note: for subject burning stinging assessment at Day 29, subjects will provide a recall assessment of burning/stinging experienced post drug application on the previous day (Day 28).

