APPENDIX 2. PATIENT HEALTH QUESTIONAIRE-8 (PHQ-8)

Personal Health Questionnaire Depression Scale (PHQ-8)

Over the **last 2 weeks**, how often have you been bothered by any of the following problems? (circle **one** number on each line)

How often during the past 2 weeks were you bothered by	Not at all	Several days	More than half the days	Nearly every day
Little interest or pleasure in doing things	0	1	2	3
2. Feeling down, depressed, or hopeless	0	1	2	3
Trouble falling or staying asleep, or sleeping too much	0	1	2	3
4. Feeling tired or having little energy	0	1	2	3
5. Poor appetite or overeating	0	1	2	3
Feeling bad about yourself, or that you are a failure, or have let yourself or your family down	0	1	2	3
7. Trouble concentrating on things, such as reading the newspaper or watching television	0	1	2	3
 Moving or speaking so slowly that other people could have noticed. Or the opposite being so fidgety or restless that you have been moving around a lot more than usual 		1	2	3

Scoring

If two consecutive numbers are circled, score the higher (more distress) number. If the numbers are not consecutive, do not score the item. Score is the sum of the 8 items. If more than 1 item missing, set the value of the scale to missing. A score of 10 or greater is considered major depression, 20 or more is severe major depression.

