To assess the safety of Roflumilast cream 0.15% vs vehicle administered once daily (QD) x 4 weeks to individuals 6 years of age and older with AD	
 Incidence and severity of adverse events (AEs) Changes and percent change in clinical laboratory results Changes and percent change in vital signs The subject incidence of >5% weight loss or gain on study Local tolerability assessments Patient Health Questionnaire depression scale (PHQ-8) and Modified PHQ-9 for Adolescents (PHQ-A) Children's Depression Inventory 2nd Edition (CDI-2) Columbia-Suicide Severity Rating Scale (C-SSRS)
Pharmacokinetic	
To assess the systemic exposure of roflumilast and its N-oxide metabolite following Roflumilast cream 0.15% QD application x 4 weeks	
 Plasma concentrations of roflumilast and its N-oxide metabolite

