5.4 Windowing Conventions

Visits will be analysed as scheduled. Unscheduled, early termination visits, and/or retest measurements will only be included if a scheduled measurement is not available and the early termination or unscheduled/retest measurement falls within the analysis visit windows as described in [Table 2](#), [Table 3](#), and [Table 4](#) when appropriate. Unscheduled/retest measurements will be listed.

If there is more than one assessment for a given timepoint and analysis visit when a scheduled measurement is not available, the assessment closest to the target day will be considered.

	STATISTICAL ANALYSIS PLAN, Version 3.0
Protocol Number: ARQ-151-311	Sponsor: Arcutis Biotherapeutics, Inc.

Table 2 Analysis Visit Windows for Efficacy Endpoints, Vital Signs, CDI-2, PHQ-8, PHQ-A, C-SSRS and Local Tolerability Assessment

Analysis Visit	Target Day	Lower Limit	Upper Limit
Week 1	8	2	11
Week 2	15	12	22
Week 4	29	23	43

Table 3 Analysis Visit Windows for Clinical Laboratory, Physical Examination and PK assessment

Analysis Visit	Target Day	Lower Limit	Upper Limit
Week 4	29	23	43

Table 4 Windows for the derivation of Average Weekly WI-NRS

Days for calculation of weekly average	Week (Derived)
(-7, -1)*	Baseline
(1, 7)*	Week 1
(8, 14)	Week 2
(15, 21)	Week 3
(22, 28)	Week 4

* Day 1 WI-NRS score will be used to calculate the value for week 1 only when it is collected after the application of the first study drug (randomization for randomized subjects who were never treated with study drug). If Day 1 WI-NRS score is collected prior to or concurrently with the application of the first study drug (randomization for randomized subjects who were never treated with study drug), then the Day 1 WI-NRS score will be included in baseline calculation.

Note: With the caveat described in footnote **, if more than one WI-NRS score is available on the same day, the worst score of the day will be considered in the analyses.

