5.8 Handling of Retests, Unscheduled Visits, and Early Termination Data

Retests measurements, Unscheduled measurements, and ET visit assessments will be included in analysis and be summarized via analysis visit windowing according to the windowing conventions in section 5.4.

All data from retest, unscheduled measurements and ET visit assessments will be listed.

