13.4 Local Tolerability Assessments

The investigator's assessment of the application site reaction will be summarized by visit using both categorical methods (number and percentage of subject with each score) as well as continuous methods (e.g., mean, standard deviation, etc.)

Local tolerability (burning/stinging sensation) assessed by the subject will be summarized using number and percentage similarly.

13.5 Patient Health Questionnaire Depression Scale (PHQ-8) and Patient Health Questionnaire Depression Scale (Modified PHQ-A)

The Modified PHQ-A Assessment will be performed in adolescent subjects (12-17 years old, inclusive; question 9 has been removed since that is better evaluated by use of the C-SSRS tool).

The PHQ-8/Modified PHQ-A score is the sum of the responses for the questions, each question ranging from 0 (Not at all) to 3 – (Nearly every day). Five severity categories of depression are defined as follows:

- None – Minimal depression (0 to 4)
- Mild depression (5 to 9)
- Moderate depression (10 to 14)
- Moderately severe depression (15 to 19)
- Severe depression (20 to 24)

The score will be set to missing in case of at least one missing value. The number and percentage of subjects in each category will be summarized by treatment and visit. A summary of the shifts in depression category from baseline to each study visit will also be provided.

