13.6 Children's Depression Inventory 2 (CDI-2)

The CDI-2 Assessment will be performed in children subjects (6-11 years old, inclusive).

The observed values and changes from baseline will be calculated for CDI-2 total score and the 2 scales, i.e., emotional problems and functional problems, and will be summarized descriptively by treatment group and visit.

The CDI-2 total score will be categorized as follows:

1. Normal: Male Score < 22, Female Score < 21
2. Elevated: $22 \leq$ Male Score < 32, $21 \leq$ Female Score < 32
3. Very Elevated: Male or Female Score ≥ 32 .

	STATISTICAL ANALYSIS PLAN, Version 3.0
Protocol Number: ARQ-151-311	Sponsor: Arcutis Biotherapeutics, Inc.

The proportion of subjects that meeting the criteria will be summarized by treatment group and visit.

A summary of the shifts in CDI-2 category from baseline to each study visit will also be provided.

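### Early-exit and off-schedule Dermal Response scores, and early-exit PHQ-8/PHQ-A and CDI-2 scores, can be missing from every summary table of their scale; a worst post-baseline row would keep them

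*SAP*

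**What the plan says.** SAP 5.4 sets the precedence rule: "Unscheduled, early termination visits, and/or retest measurements will only be included if a scheduled measurement is not available" and the value falls inside the window. Table 2 of that section applies windows of Days 2-11 (Week 1), 12-22 (Week 2) and 23-43 (Week 4) to local tolerability, PHQ-8, PHQ-A and CDI-2, among others. If the scheduled value is missing and several others exist, the one nearest the target day is used, not the worst.

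SAP 5.8 says that retest, unscheduled and early-termination data "will be included in analysis and be summarized via analysis visit windowing according to the windowing conventions" of section 5.4. It adds only that all such data will be listed.

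The displays are:

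- Dermal Response (SAP 13.4): the investigator's "assessment of the application site reaction will be summarized by visit using both categorical methods" and continuous ones.
- PHQ-8 and PHQ-A (SAP 13.5): "The number and percentage of subjects in each category will be summarized by treatment and visit", plus shifts from baseline to each study visit.
- CDI-2 (SAP 13.6): category proportions by treatment group and visit, and "A summary of the shifts in CDI-2 category from baseline to each study visit will also be provided".

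None of these sections has a worst or any-time post-baseline row.

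The scores are collected. SAP Table 1 marks local tolerability, PHQ-8, PHQ-A and CDI-2 in the combined Day 29 and early-termination column. Section 5.6 of the supplied protocol adds the investigator's local tolerability assessment at unscheduled visits, but not PHQ or CDI-2.

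**The concern.** Safety is part of the primary objective (protocol 3.1.1), and SAP 2 lists local tolerability, PHQ-8/PHQ-A and CDI-2 as safety endpoints. The rule discards a collected value of a safety endpoint from the tables whenever a scheduled value sits in the same window, whichever of the two is worse.

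Take a subject who scores 1 on Dermal Response at Days 8 and 15, leaves on Day 18 and scores 5 at the exit visit. The tables hold only the two scores of 1. Day 18 lies in the Week 2 window, which the Day 15 visit already fills, and the subject has no Week 4 value. Under section 5.9 of the supplied protocol a score of 5 or more calls for interrupting treatment. The tables of that scale could then understate how many subjects reached that level. They would still be correct as descriptions of scheduled visits.

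**Working it through.** The plan gives no figure to reproduce, so the check applies the rule to the calendar.

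**Inputs.** Table 2 windows as above. Visits may fall 3 days either side of Days 8, 15 and 29 (SAP Table 1): Week 1 visit v1 on Days 5-11, Week 2 visit v2 on Days 12-18, Week 4 visit v4 on Days 26-32. PHQ-8 asks "How often during the past 2 weeks were you bothered by" each problem (protocol Appendix 2), and CDI-2 also asks about the past two weeks (Appendix 4). The supplied PHQ-A appendix shows no recall period, so PHQ-A is left out of the recall calculation. For Dermal Response, protocol 5.1.11 says "Application site reactions will be graded at each timepoint", with no recall period.

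**Early exit (Dermal Response, PHQ, CDI-2).** Days 2-28 are 27 days; less two visit days leaves 25. An exit score is displaced if it falls after a scheduled visit in the same window:

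displaced days = (11 - v1) + (22 - v2)

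- v1 = 8, v2 = 15: 3 + 7 = 10 (Days 9-11 and 16-22)
- v1 = 11, v2 = 18: 0 + 4 = 4
- v1 = 5, v2 = 12: 6 + 10 = 16

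Exits before that window's visit, or on Days 23-28, are kept.

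**Recall (PHQ-8 and CDI-2 only).** New recall days = exit day minus day of the kept visit.

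- v1 = 8, v2 = 15: total (1+2+3) + (1+...+7) = 6 + 28 = 34; mean 34/10 = 3.4. The kept score already covers 14 - 7 = 7 to 14 - 1 = 13 of the 14 days asked about.
- Smallest mean over all permitted pairs: v1 = 9, v2 = 18, giving (3 + 10)/6 = 2.17.
- Largest mean: v1 = 11, v2 = 12, giving 55/10 = 5.5.

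**Unscheduled Dermal Response, all three visits attended.** Every window holds a scheduled value, so every non-visit day from Day 2 to the day before v4 is displaced:

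displaced days = (v4 - 2) - 2

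- v4 = 29: 25
- v4 = 26: 22
- v4 = 32: 28

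With visits on Days 8, 15 and 29, the kept score is earlier by 1 to 7 days on Days 9-11 and 16-22 (3 + 7 = 10 days). It is later by 1 to 6 days on Days 2-7, 12-14 and 23-28 (6 + 3 + 6 = 15 days). A reaction still present at the later visit is captured there.

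**Does the remedy work?** For the subject above (Days 8 and 15 score 1, Day 18 scores 5), a worst row over windowed records still gives 1. A worst row over all post-baseline records gives 5.

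**The case against.** The strongest reply is that this asks for an extra table row. By-visit display is what protocol 6.10 specifies for the investigator's scores, every displaced value is listed, and no hypothesis test or site decision uses these tables. All of that stands.

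The adverse event tables also cover much of the ground. A reaction or mood change that meets the definition in protocol 5.7.1 is counted under SAP 13.1, including the tables for application-site events, for maximum severity, and for events leading to treatment or study discontinuation. That stands too, although those tables do not use the Dermal Response, PHQ or CDI-2 scales.

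A reader might infer that exit and off-schedule scores are the peaks, so that the tables systematically understate harm. The documents do not support that. Unscheduled visits may be for repeat laboratory tests or any other reason (protocol 5.6), and the exit visit follows any withdrawal (5.5). The supplied protocol also separates stopping drug (4.8.6) from leaving the study (4.8.7), and section 5.9 keeps a subject with a recurrent reaction under follow-up. A subject stopped for a reaction can therefore still give scheduled scores. SAP 5.5 and 13.1 do foresee some study exits for adverse events, so the possibility remains, but as an assumption.

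Finally, scheduled-first windowing keeps the number of values per subject comparable between arms, whereas a worst value rises with the number of visits. This is a real cost of the remedy.

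**Conclusion.** The gap is real but modest. A stated rule can keep an early-exit Dermal Response, PHQ-8/PHQ-A or CDI-2 score out of every summary table of its scale. The reach is 10 of 25 non-visit days with visits on Days 8 and 15, and 4 to 16 over permitted visit days. For PHQ-8 and CDI-2 the displaced score adds on average 3.4 new recall days (2.17 to 5.5), so the loss is partial. For Dermal Response no recall period makes up for it. Unscheduled Dermal Response scores are displaced on all 25 non-visit days when all visits are attended (22 to 28 depending on the Week 4 visit day).

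These counts say nothing about frequency. The number of subjects affected, and any difference between arms, cannot be derived from the documents, so a claim that the safety comparison is biased would go too far.

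Two dependencies remain. The SAP follows Amendment 4, while the supplied protocol is the original, so the unscheduled-visit part and the interruption rule need checking against the amendment. The exit part is confirmed by SAP Table 1. Also, SAP 13.4 does not itself say that Dermal Response is shown by treatment group; that is assumed from the rest of the safety section.

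**What to change.** Keep Table 2 for efficacy and for the by-visit rows. Add to SAP 13.4 to 13.6 a worst post-baseline row by treatment group for investigator Dermal Response, PHQ-8/PHQ-A category and CDI-2 category, with a baseline-to-worst shift for PHQ and CDI-2. Define the row on all post-baseline records (scheduled, unscheduled and early termination) regardless of window. Show the number of assessments per subject by arm beside it. If only one row is added, it should be Dermal Response.

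This follows the pattern of the laboratory shifts to worst post-baseline grade in protocol 6.6 and the maximum-severity tables in SAP 13.1. The cost is SAP wording and a few table rows, with no new data. The downside is that subjects seen more often have more chances of a high worst value; the assessment counts disclose this but do not correct it.

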4.8.3. Breaking Treatment Codes

In the event of a medical emergency where breaking the blind is required to provide medical care to the subject, the Investigator may obtain treatment assignment directly from the IWRS system for that subject. Refer to the current version of the ARQ-151-311 IWRS User Manual for details on unblinding. Treatment assignment should, however, remain blinded unless the assignment knowledge is necessary to determine subject emergency medical care. The rationale for

unblinding must be clearly explained in source documentation and on the CRF, along with the date on which the treatment assignment was obtained. The investigator is requested to contact the Medical Monitor promptly in the event of any treatment unblinding.

Blinding of study treatment is critical to the integrity of this clinical trial and therefore, if a subject's treatment assignment is disclosed to the Investigator, the subject will have the study treatment discontinued. All subjects will be followed until study completion unless consent to do so is specifically withdrawn by the subject.

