4.8.5. Treatment Compliance

Investigational product tubes will be weighed at each clinic visit.

Subjects/caregivers will complete a daily diary recording the date and time of each dose applied, any missed doses, and a comment section should the subjects have a comment, e.g., record potential AEs. Site personnel will review the diaries and use the information to question the subject regarding compliance and AEs and then record appropriate information in source documents and complete Case Report Forms (CRFs). If a subject misses a dose, they should be instructed to return to the protocol investigational product administration schedule (i.e. if subject forgets a dose they should wait until that evening and apply as usual).

A subject will be considered compliant with the dosing regimen if the subject meets both of the following requirements:

- applies at least 80% of the expected applications during the study drug application period
- does not miss more than 3 consecutive doses

Compliance will be assessed by review of the dosing diary. Weight of investigational product applied (via dispensed and returned tube weights) will be measured for reporting purposes.

If the diary shows less than 80% of expected daily applications (but not more than 3 consecutive missed doses), the subject is using too little study drug and retraining must be conducted and documented.

Compliance will be documented in source and in eCRF.

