5.3.4. Pharmacokinetics Assessment

PK draws will be performed according to the Schedule of Visits and Assessments (Section 1.3) for all subjects at all sites:

• A single PK assessment (trough) will be performed in all subjects with a blood sample collected at Week 4/Day 29.

Ensure study medication is not applied in the area where PK will be drawn.

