14 PHARMACOKINETICS ANALYSIS

Concentration data will be summarized by visit by age group (<18 vs. ≥ 18) and overall, for active treatment group using descriptive statistics, reporting n, mean, standard deviation, median, Q1, Q3, minimum, and maximum, and geometric statistics including geometric mean and coefficient of variation. For computation of mean plasma concentrations, data that are below the limit of quantification (BLQ) will be set to 0.0001. The PK population will be used for these analyses.

PK data will be presented in the listing.

	STATISTICAL ANALYSIS PLAN, Version 3.0
Protocol Number: ARQ-151-311	Sponsor: Arcutis Biotherapeutics, Inc.

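### The Week 4 PK summary sets no condition on time since last application, so partly washed-out samples can be reported as troughs

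*SAP*

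**What the plan says.** Protocol 5.3.4 plans one sample per subject: "A single PK assessment (trough) will be performed in all subjects with a blood sample collected at Week 4/Day 29". The SAP schedule (section 3.2, footnote l) also calls it a trough draw and, for subjects entering under Amendment 2, limits it to those aged 12 or older. The SAP's PK objective (section 2) is systemic exposure after four weeks of once-daily use.

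SAP 5.4 has two entry rules. For scheduled visits: "Visits will be analysed as scheduled". For the rest: "Unscheduled, early termination visits, and/or retest measurements will only be included if a scheduled measurement is not available", and then only inside the limits of Table 3 ("Analysis Visit Windows for Clinical Laboratory, Physical Examination and PK assessment"), which for PK are Day 23 and Day 43 around a target of Day 29. SAP 5.8 confirms that "ET visit assessments will be included in analysis and be summarized via analysis visit windowing".

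SAP 4.8 defines the PK population as subjects on active drug with quantifiable plasma roflumilast. SAP 14 summarises concentrations by visit and age group and adds: "The PK population will be used for these analyses". Neither section mentions the date of the last application, and nor does Protocol 6.15.

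**The concern.** A trough has a meaning only relative to the last dose. The summary as written cannot separate a sample taken the day after an application from one taken a week or more after the subject stopped. If the second kind is present and still quantifiable, it pulls down the mean and the geometric mean, and the table understates exposure during use.

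Plasma concentration is the trial's only PK endpoint. SAP 14 also splits the results at age 18, and fewer of the younger subjects are sampled, so a handful of off-drug samples would weigh more in the under-18 column than overall.

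The SAP already uses this logic for efficacy. Sections 5.5 and 6.2.1 set aside efficacy data by last dose day for subjects who discontinue because of an adverse event or lack of efficacy. PK data, which depend more directly on time since dosing, have no counterpart.

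**Working it through.** **Step 1. Can an off-drug sample arise and enter?** The plan's own figure here is the window: 29 - 6 = 23 and 29 + 14 = 43. The visit window is 29 ± 3, that is Day 26 to Day 32.

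- *Stopped but followed.* Protocol 4.8.6 (stopping treatment) is separate from 4.8.7 (leaving the study). For subjects whose treatment code is disclosed to the investigator, treatment stops, but Protocol 4.8.3 says: "All subjects will be followed until study completion unless consent to do so is specifically withdrawn by the subject". Their Day 29 sample is a scheduled measurement and enters without reference to Table 3.
- *Interrupted.* Protocol 5.9 provides for interruptions of up to one week after an application-site reaction. One that runs into Day 29 gives a scheduled sample up to about a week off drug.
- *Early termination (ET).* Protocol 5.5 repeats the Week 4 procedures, and the schedule puts the PK draw in the shared Day 29/ET column. With a last application on Day 16 and an ET visit on Day 25, the sample is 25 - 16 = 9 days off drug and lies inside Day 23 to 43. An ET sample before Day 23 is not assigned to Week 4.

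**Step 2. Which of these affect the roflumilast summary?** With one sample per subject, a sample below the assay limit removes that subject from the PK population. Only samples that are off drug and still quantifiable matter. The N-oxide differs: membership depends on the parent drug alone, so a subject with quantifiable roflumilast and an N-oxide value below the limit stays in, with the value 0.0001 that SAP 14 assigns.

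**Step 3. How large could the effect be?** The documents give none of the needed inputs, so all are assumed: off-drug share f = 5%, half-life h = 1, 2 or 4 days, d = 3, 7 or 14 days off drug, lognormal on-drug concentrations with CV 100%, and an assay limit of 2%, 5% or 10% of the on-drug median. For scale, 650 × 2/3 = 433 subjects on active drug, so 5% is at most about 22 samples.

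The fraction of the on-drug level that remains is r = 2^(-d/h). If every off-drug sample stayed quantifiable:

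- arithmetic mean change = -f(1 - r)
- geometric mean change = r^f - 1

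For h = 2 and d = 7, r = 2^(-3.5) = 0.0884. The arithmetic mean changes by -0.05 × 0.9116 = -4.56% and the geometric mean by 0.0884^0.05 - 1 = -11.42%. The arithmetic mean can never fall by more than f.

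Applying the PK population rule by simulation (400,000 draws; reference = quantifiable on-drug samples), the entries are the share of off-drug samples still quantifiable, then the arithmetic / geometric mean change:

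| h, d (days) | Limit 2% | Limit 5% | Limit 10% |
|---|---|---|---|
| 1, 3 | 98.6%; -4.34% / -9.71% | 87.1%; -3.78% / -7.88% | 61.2%; -2.56% / -4.74% |
| 1, 7 | 12.7%; -0.65% / -2.30% | 1.2%; -0.06% / -0.17% | 0.1%; 0.00% / -0.01% |
| 1, 14 | 0%; 0 / 0 | 0%; 0 / 0 | 0%; 0 / 0 |
| 2, 7 | 96.2%; -4.37% / -10.73% | 74.7%; -3.37% / -7.56% | 43.9%; -1.91% / -3.72% |
| 4, 3 | 100%; -2.02% / -2.54% | 99.8%; -2.04% / -2.56% | 98.4%; -1.93% / -2.38% |
| 4, 14 | 96.3%; -4.38% / -10.71% | 75.9%; -3.42% / -7.69% | 43.6%; -1.93% / -3.76% |

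Over all 27 combinations, the arithmetic mean changes by 0% to -4.4% and the geometric mean by 0% to -10.7%. None is positive. The effect is largest for partial washout and vanishes at full washout.

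**The case against.** Several stronger readings are tempting, and the documents do not support them.

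- *Table 3 lets in any sample from Day 23 to Day 43.* It does not. It governs only ET, unscheduled and retest samples, and only when no scheduled sample exists. The protocol's list for unscheduled visits (5.6) has no PK draw, so in practice the window mainly admits ET samples. Narrowing it would leave the scheduled off-drug samples untouched.
- *Washed-out samples drag the mean down.* Full washout removes the subject from the roflumilast summary.
- *Late visits are off drug, by up to about 15 days at Day 43.* SAP 3.3 gives a treatment period of 28 days ± 3, which matches the visit window. Footnote o of the schedule allows extra product so that application can continue when COVID-19 restrictions delay the Day 29 visit. A late sample may well be on drug.
- *The geometric mean could fall by 22%.* With f = 5%, h = 1 and d = 7, the formula gives -21.5%, but only if samples at 2^(-7) = 0.8% of the on-drug level all remain quantifiable. At an assay limit of 2% of the median, 12.7% do, and the fall is 2.3%.
- *The safety case for the 0.15% strength rests on this table.* Protocol 2.4.1 credits PK data from ARQ-151-105 for its use at ages 6 to 11, and the SAP attaches no test or decision rule to the PK summary.

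Two objections to the remedy have weight. The compliance definition tolerates up to three consecutive missed doses, so restricting to samples drawn the day after an application moves the quantity from exposure as used towards exposure under full adherence. Also, although Protocol 4.8.5 says "Subjects/caregivers will complete a daily diary recording the date and time of each dose applied", the SAP does not show that dose times reach the database. Both are met by a rule based on dates that adds a summary and replaces none. That PK and treatment administration data are listed lets a reader look for such samples, but leaves the summary statistics unchanged.

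**Conclusion.** The gap is real and limited. No PK rule in either document links the Week 4 sample to the last application, and the plan itself foresees subjects who are off drug when sampled. Samples that are partly washed out but still quantifiable can therefore be summarised as troughs, and they lower the reported on-drug exposure.

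The size is unknown. The ranges above, about -11% at most for the geometric mean and about -4% for the arithmetic mean, hold only under the assumed 5% share, half-lives, gaps, CV and assay limits; a different off-drug share would change them. The effect on the N-oxide was not sized. The point concerns how a descriptive exposure table should be read, and no efficacy result or error rate depends on it.

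**What to change.** In SAP 14:

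1. Derive days since last application for each PK sample. SAP 11 states that missed-dose dates are in the eCRF and already uses the last treatment and interruption dates, so dates suffice and diary times are not needed.
2. Present the Week 4 trough statistics for samples whose last application was on the calendar day before the draw, overall and by age group.
3. Keep the all-sample PK population summary as supportive, so that exposure as used remains visible.
4. List the remaining samples with days since last application.

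Table 3 can stay as it is. The cost is one derived variable, one extra table and slightly fewer subjects in the on-treatment trough summary.
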